#### **All Subjects:**

Nivolumab and ipilimumab administration will continue for 2 years or until progression of disease, unacceptable toxicity, death, or another protocol criterion for subject withdrawal is met, whichever comes first. One treatment cycle will be defined as 42 days (6 weeks), corresponding to 3 doses of nivolumab and one dose of ipilimumab.

Subjects will be evaluated every 8 weeks with radiographic imaging to assess response to treatment. Disease assessments on study will be made using standard Response Assessment for Neuro-Oncology (RANO) criteria for high-grade gliomas. However, non-traditional Immunotherapy Response Assessment for Neuro-Oncology (iRANO) criteria (Appendix 3), which is based on the immune-related response criteria and the RANO criteria for brain tumor response assessment, may be considered for patient management. The primary efficacy endpoint will be overall survival at 1 year. Adverse events will be monitored throughout the trial and graded in severity according to the guidelines outlined in the NCI Common Terminology Criteria for Adverse Events (CTCAE) version 4.03.

CONFIDENTIAL

This material is the property of the NYU School of Medicine. Do not disclose or use except as authorized in writing by the study sponsor

End of treatment assessments will be performed within 7 days after last drug administration or within 7 days after decision to end treatment. In addition, site visits and safety laboratories are to be performed at 30 days ( $\pm 7$  days) and 90 days ( $\pm 14$  days) after the last study drug is given, unless the subject is unable to travel due to deteriorating medical condition, due to the potential risk for delayed immune-related toxicities. Post-treatment, all participants will be followed until resolution or stabilization of any serious or reportable adverse events occurring during treatment or starting within 100 days of the last nivolumab infusion and 90 days of the last ipilimumab infusion. Assessments may continue for ongoing reportable adverse events.

In this study, survival is a key endpoint. In addition, there is potential risk for delayed immune-related toxicities with study drug. Therefore, post study follow-up is of critical importance and is essential to preserving subject safety and the integrity of the study. Subjects who discontinue study drug must continue to be followed for collection of outcome and/or survival follow-up data until death, withdrawal of permission to record at least survival data, or subject is lost to follow-up.

Following the 90-day post-drug visit, all subjects will be contacted every 3 months ( $\pm 14$  days) to assess for study-treatment related toxicities, initiation of any new anti-cancer treatments, and survival status. Contact may be performed by a site visit, telephone contact, e-mail, or mail.

Expected duration of subject participation is 10 months, which is beyond the median progression-free survival achieved with standard therapy for newly diagnosed GBM with unmethylated *MGMT* (median PFS of 6 months with standard therapy).

Specific procedures to be performed during the study, as well as their required times and associated visit windows, are outlined in the Study Procedures and Schedule of Events (Appendix 1).

### **3.2 Primary Study Endpoint**

#### **Main Study Cohort:**

- To determine the overall survival at 1 year (1-yr OS) of adults with newly diagnosed, *MGMT* unmethylated GBM administered nivolumab, ipilimumab and hypofractionated RT.

#### **Surgical Study Cohort:**

- The primary objective is safety, feasibility and tolerability

### **3.3 Secondary Study Endpoints**

#### **Main Study Cohort:**

- To assess safety and tolerability
- Estimate additional measures of efficacy, including 2-year OS, median OS, median PFS, radiographic response rate, and median duration of response

#### **Surgical Study Cohort:**

- Estimate measures of efficacy, including 1-year OS, 2-year OS, median OS, median PFS, radiographic response rate, and median duration of response

### **3.4 Exploratory Endpoints**

#### **Both Study Cohorts:**

- Association of 1-yr OS with: tumor tissue biomarkers including mutation burden, neoantigen load, immune marker expression [e.g. PD-L1, lymphocyte activation gene 3 (LAG3), indoleamine-2,3-

CONFIDENTIAL

This material is the property of the NYU School of Medicine. Do not disclose or use except as authorized in writing by the study sponsor

dioxygenase (IDO) and T-cell immunoglobulin and mucin domain 3 (TIM3)], and PD-1+ tumor infiltrating lymphocytes (TILs).

- Association of 1-yr OS with baseline and change at 6 weeks in levels of circulating biomarkers, including: regulatory T cells ( $T_{reg}$ ); myeloid-derived suppressor cells (MDSC); and immune cell populations as profiled by high-parameter flow cytometry that simultaneously quantifies expression of proteins related to checkpoint inhibitors (PD1, CTLA4, TIM3, TIGIT, 41BB, CD150, LAG3, BTLA), differentiation status (CD45RA, CCR7, CD57, CD95, CD127), and other traits (CD25, IL12R, CXCR3, CXCR6).
- Effect of study regimen on total lymphocyte counts (TLC) and CD4 counts at fixed timepoints for up to 1 year compared to baseline.
- Explore whether sodium MRI, a non-invasive surrogate measure of cell death in tissue, can differentiate between treatment-related cell death/necrosis ("pseudoprogression") versus tumor progression and serve as a potential non-invasive pharmacodynamic biomarker.

### **3.5 Primary Safety Endpoints**

#### **3.5.1 Phase II Safety Analysis**

For the phase II portion of the study, we consider a rate of unacceptable toxicity of 40% or greater (defined as CTCAE grade 3, grade 4, or intolerable grade 2 toxicity that is possibly, probably, or definitely related to study therapy) to be unacceptable. Intolerable grade 2 toxicity will be defined as any grade 2 toxicity that results in study discontinuation. Monitoring for toxicity will follow a Bayesian-based rule for the probability that the rate of unacceptable toxicity exceeds a maximal tolerated level of 40%. We will assume a *Beta*(2,3) prior, which is prior information equivalent to two unacceptable toxicities observed in 5 treated patients. This minimally informative prior is justified as there is some clinical experience with the combination therapy. Early termination for unacceptable toxicity will be considered based on a posterior probability (in parentheses), that the unacceptable toxicity rate exceeds 30%. Toxicity will be carefully monitored in the 24 Phase II patients. Termination will be considered if unacceptable toxicity is observed in: 2 of 3 patients (0.71), 4 of 6 patients (0.83), 5 of 9 patients (0.77), 7 of 12 patients (0.86), 8 of 15 patients (0.81), 9 of 18 patients (0.77), 11 of 21 patients (0.85), or 12 of 24 patients (0.81).

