### *Endpoints:*

1yr-OS and radiographic response rates will be estimated with exact 95% confidence intervals; with 24 patients, a 95% CI will be no more than 0.4 units wide for the main study cohort. PFS, defined as the time between treatment initiation and first occurrence of disease progression or death, will be censored at last follow-up if the patient remained alive without disease progression. OS will be determined from the time of treatment initiation until the time of death, with OS being censored at last follow-up if the patient remained alive. The Kaplan-Meier curves will be used to summarize PFS and OS and to estimate the medians.

Adverse events will be graded using CTCAE version 4.03. All subjects who initiate therapy (receive at least one dose of ipilimumab and nivolumab and/or radiotherapy) will be evaluated for safety. A Bayesian monitoring approach will be applied to assess safety throughout the Phase II trial with pre-defined stopping rules.

CONFIDENTIAL

This material is the property of the NYU School of Medicine. Do not disclose or use except as authorized in writing by the study sponsor

CONFIDENTIAL

This material is the property of the NYU School of Medicine. Do not disclose or use except as authorized in writing by the study sponsor

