### 7.2 Statistical Methods and Sample Size Determination

#### 7.2.1 Safety

The Safety Lead-In portion of the study will include the first 6 subjects enrolled on the Main Study Cohort. The exact number of patients enrolled in the entire study will depend on the number of protocol-defined DLTs observed and the possibility of opening additional cohorts at modified nivolumab and/or ipilimumab prescriptions as described in Section 6.1.1 (Safety Lead-In). Data for the Safety Lead-In will be summarized using descriptive statistics.

Adverse events will be graded using CTCAE version 4.03. Safety summaries will be reported for both the Safety Lead-In and the phase II trial. All subjects who received at least one dose of study drug and/or radiation will be used for the analysis of safety data in this study. Safety and tolerability will be assessed

CONFIDENTIAL

This material is the property of the NYU School of Medicine. Do not disclose or use except as authorized in writing by the study sponsor

by clinical review of all relevant parameters including adverse experiences (AEs), laboratory tests, and vital signs.

Additionally, specific immune-related adverse experiences (irAEs, as defined Section 6.2.1) will be collected and summarized in separate tables from other AEs by toxicity grade and will include the counts, percentage, and 95% CI.

Adverse events (specific terms as well as system organ class terms) and predefined limits of change in laboratory, and vital sign parameters will be summarized with descriptive statistics (counts, percentage, mean, standard deviation, etc.). Continuous measures such as changes from baseline in laboratory, and vital signs parameters will be summarized using descriptive statistics (mean, standard deviation, etc.) for baseline, on-treatment, and change from baseline values.

For toxicity monitoring statistical methods, see the Primary Safety Endpoints in Section 3.5.

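### The toxicity stopping rule is labelled as a 30% limit, but all eight printed posterior probabilities are for the 40% limit stated twice in the same section

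*Combined protocol and SAP*

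**What the plan says.** Section 3.5.1 of the combined protocol and SAP gives the limit three times.

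- The opening definition: "we consider a rate of unacceptable toxicity of 40% or greater".
- The monitoring rule: it concerns the "probability that the rate of unacceptable toxicity exceeds a maximal tolerated level of 40" per cent.
- The sentence that explains the bracketed figures: "Early termination for unacceptable toxicity will be considered based on a posterior probability (in parentheses), that the unacceptable toxicity rate exceeds 30" per cent.

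The prior is Beta(2,3), described as "prior information equivalent to two unacceptable toxicities observed in 5 treated patients". Termination is to be considered at these counts, each with its posterior probability in brackets:

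- "2 of 3 patients (0.71), 4 of 6 patients (0.83), 5 of 9 patients (0.77), 7 of 12 patients (0.86"), then
- "8 of 15 patients (0.81), 9 of 18 patients (0.77), 11 of 21 patients (0.85), or 12 of 24 patients (0.81").

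No other section gives the limit. The synopsis says only that "A Bayesian monitoring approach will be applied to assess safety throughout the Phase II trial with pre-defined stopping rules". Section 7.2.1 refers back: "For toxicity monitoring statistical methods, see the Primary Safety Endpoints in Section 3.5". Section 8.5 (Stopping Rules) also points to Section 3.5.

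**The concern.** The probability that a rate exceeds 30% and the probability that it exceeds 40% are different quantities, and one set of bracketed values cannot be both. The 30% stands in the sentence that tells the monitoring committee what those values mean.

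Two things could go wrong. First, termination is only to be considered, so the committee weighs the probability. Taking the sentence at its word, it would understate how likely the rate is to exceed 30%. Second, a statistician who rebuilds the rule from the sentence would not recover the printed figures and, at comparable cut-offs, would get lower trigger counts. The citation attached to the rule does not resolve the question: it is numbered 90, and entry 90 in Section 14 is a tool for predicting MHC class I binding.

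**Working it through.** **Inputs**, all from Section 3.5.1: prior Beta(2,3); x unacceptable toxicities in n patients at each of the eight looks; the printed probabilities; candidate limits of 40% and 30%.

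**Formula.** With a binomial likelihood the posterior is Beta(2 + x, 3 + n − x). The quantity needed is its upper tail beyond the limit t, P(rate > t).

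**Worked example.** At 2 of 3 the posterior is Beta(4, 4). P(rate > 0.40) = 0.7102, which rounds to the printed 0.71. P(rate > 0.30) = 0.8740.

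**All eight looks:**

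| Count | Posterior | Printed | P(rate > 40%) | P(rate > 30%) | 30% value minus printed |
|---|---|---|---|---|---|
| 2/3 | Beta(4,4) | 0.71 | 0.7102 | 0.8740 | 0.164 |
| 4/6 | Beta(6,5) | 0.83 | 0.8338 | 0.9527 | 0.123 |
| 5/9 | Beta(7,7) | 0.77 | 0.7712 | 0.9376 | 0.168 |
| 7/12 | Beta(9,8) | 0.86 | 0.8577 | 0.9743 | 0.114 |
| 8/15 | Beta(10,10) | 0.81 | 0.8139 | 0.9674 | 0.157 |
| 9/18 | Beta(11,12) | 0.77 | 0.7720 | 0.9613 | 0.191 |
| 11/21 | Beta(13,13) | 0.85 | 0.8462 | 0.9825 | 0.133 |
| 12/24 | Beta(14,15) | 0.81 | 0.8132 | 0.9792 | 0.169 |

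The 40% column rounds to the printed value at every look. The 30% column does so at none.

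**Which limits fit the print?** Allow each printed value its rounding of ±0.005 and solve for t. In the order of the table, the intervals are 0.3975–0.4027, 0.3993–0.4052, 0.3983–0.4027, 0.3961–0.4014, 0.3996–0.4036, 0.3990–0.4023, 0.3964–0.4005 and 0.3994–0.4027. They overlap only from 0.3996 to 0.4005.

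**What the wrong label conveys.** Read as written, the chance that the rate is 30% or lower is one minus the printed value: 0.29, 0.17, 0.23, 0.14, 0.19, 0.23, 0.15, 0.19. Under the protocol's own prior it is 0.13, 0.05, 0.06, 0.03, 0.03, 0.04, 0.02, 0.02. The gap is widest at 9 of 18 (0.23 against 0.04).

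**What a rebuild at 30% would give.** The protocol states no posterior cut-off, so one has to be assumed. At cut-offs of 0.70, 0.71, 0.75, 0.77 and 0.80 the smallest triggering counts are the same: 2/3, 3/6, 4/9, 5/12, 6/15, 7/18, 8/21, 9/24. Every look after the first would then trigger one to three events earlier than printed. A cut-off of 0.90 gives 3/3, 4/6, 5/9, 6/12, 7/15, 8/18, 9/21, 11/24.

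**The case against.** The strongest reply is that the error barely touches conduct. The rule is operated through its counts, which are printed; the bracketed values only annotate them. Two of the three statements of the limit already say 40%, and the counts and probabilities agree with each other at 40%. No decision is tied to the size of the posterior. This stands as a limit on the harm: a committee that uses only the counts stops at the same points whatever the label says. It does not remove the contradiction, because the wrong figure is in the sentence that defines the stopping probability and nothing elsewhere corrects it.

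A second reply is that restoring 30% would not be a simple recalculation. That also stands. The probabilities can be recomputed at once, but new counts need a cut-off that the protocol does not give, and they would change a safety boundary. Nor can a cut-off be inferred exactly from the printed list at 40%: one low enough to trigger at 2 of 3 (0.710) would also trigger at 6 of 12 (0.716) and at 10 of 21 (0.732), and neither is listed as a trigger.

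**Conclusion.** The concern holds. The 30% in Section 3.5.1 contradicts the section's two statements of 40% and all eight of its own probabilities, by 0.11 to 0.19. The result rests only on the stated prior, the stated counts and the standard beta-binomial update; no outside figure is needed. It should be fixed because it is the stated threshold in the only full account of the trial's continuous toxicity rule. It is not more serious than that, since the explicit counts can be applied without the percentage.

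A minor, separate point of definition in the same section: the tally counts related grade 3, grade 4 and intolerable grade 2 events, which read literally leaves out related deaths (grade 5). Section 3.5.2 uses grade 3 or higher, as does the opening definition in Section 6.1.1.1, although some bullets there say only grade 3. Those sections define other events for other purposes, and Section 8.4 has the DSMC evaluate every SAE, so the consequence is small. The main finding does not depend on it.

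**What to change.** Reconcile Section 3.5.1 to a single limit.

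- **If the sponsor intends 40%,** as the other two statements and all the printed values indicate, replace 30% with 40% in the sentence on early termination. No count and no probability changes. The cost is one number in the text.
- **If the sponsor intends 30%,** bring the two 40% statements into line, recompute the eight probabilities, state the posterior cut-off and re-derive the counts from it. The calculation is short, but this is a substantive change to a safety stopping rule and should be handled as one.

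In the same edit, say whether related grade 5 events count in this tally, and correct the reference number attached to the Bayesian rule.

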### Main Study Cohort

### Surgical Study Cohort

### 3.1.2 General Study Design

This is an open label, phase II trial of nivolumab, ipilimumab and hypofractionated radiation therapy in adult patients with newly diagnosed, *MGMT* unmethylated GBM with the primary objective of determining the overall survival at 1 year.

**Safety Lead In:** The study will start with a Safety Lead-In consisting of the first 6 subjects (Section 6.1.1), which will be conducted to further define the safety and tolerability of nivolumab and ipilimumab when given in combination with hypofractionated radiotherapy in previously untreated, newly diagnosed GBM patients with unmethylated *MGMT* promoter. Note, special safety provisions are included for the first 3 subjects enrolled (see Section 6.1.1). After the first 6 subjects are enrolled, enrollment will stop and subjects will be observed for 40 days for dose-limiting toxicities (DLTs, see DLT definitions is Section 6.1.1.1). After all subjects in the Safety Lead-In cohort have completed the DLT observation period, the safety data will be reviewed by the Sponsor and the NYU DSMC. If 2 or more of the first 6 subjects in the Safety Lead-in experiences a DLT during the 40 day DLT observation period, the sponsor and the FDA, may redesign the dosing and schedule of the study treatment or will stop the study for unacceptable toxicity. If 1 or less of the first 6 subjects experiences a DLT at the end of the 28 day DLT observation period, the study will continue enrollment onto the phase II part of the study.

**Main Study Cohort:** The Phase II trial is an open-label, single-stage study at the nivolumab and ipilimumab doses and schedules determined to be safe in combination with RT in the Safety Lead-in.

The phase II trial will enroll a total of 24 subjects, including those from the safety lead-in. Monitoring of toxicity attributable to study treatment will be continually assessed during the phase II trial using a

CONFIDENTIAL

This material is the property of the NYU School of Medicine. Do not disclose or use except as authorized in writing by the study sponsor

Bayesian monitoring approach, assessing safety with the accrual of every three additional patients (see Primary Safety Endpoints, Section 3.5).

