Surgical Study Cohort: We will use a single stage design to assess safety, feasibility and therapeutic efficacy of nivolumab and ipilimumab with the first dose being administered pre-operatively and continued post-operatively in conjunction with HFRT. We will enroll 16 subjects in this cohort. Monitoring of toxicity attributable to study treatment will be continually assessed (see Primary Safety Endpoints, Section 3.5).

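### Section 3.5.1 gives no overall-toxicity boundary or counting rule for the 16 surgical-cohort patients, although Section 3.1.2 relies on Section 3.5 to monitor them

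*Combined protocol and SAP*

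**What the plan says.** Section 3.1.2 sets the surgical cohort's size, "We will enroll 16 subjects in this cohort", and then its monitoring: "Monitoring of toxicity attributable to study treatment will be continually assessed (see Primary Safety Endpoints, Section 3.5"). Section 3.2 gives that cohort's primary endpoint: "The primary objective is safety, feasibility and tolerability". The synopsis adds T-cell pathway induction as a further primary objective.

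Section 3.5.1 holds the overall-toxicity rule. It uses a Beta(2,3) prior, described as "prior information equivalent to two unacceptable toxicities observed in 5 treated patients", and lists counts at which termination will be considered: 2/3, 4/6, 5/9, 7/12, 8/15, 9/18, 11/21 and 12/24. It limits the patients monitored: "Toxicity will be carefully monitored in the 24 Phase II patients". Section 3.1.2 identifies those 24 under the main cohort: "The phase II trial will enroll a total of 24 subjects, including those from the safety lead-in", with looks described as "assessing safety with the accrual of every three additional patients".

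Section 7.2.1 places the lead-in in the main cohort: "The Safety Lead-In portion of the study will include the first 6 subjects enrolled on the Main Study Cohort". The DLT definition in Section 6.1.1.1 is for the lead-in. Section 8.5 adds no phase II rule and points back to Section 3.5. Section 3.5.2 is a one-time look at the first 12 subjects treated; it halts the trial if 4 or more have related grade 3 or higher CNS toxicity.

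**The concern.** The cross-reference leads to a rule that does not describe the patients sent to it. The table ends at 24, which is the main-cohort size; it fits neither 16 surgical patients nor 24 + 16 = 40 patients in total. Someone running the trial could count surgical patients on their own, pool them with the main cohort, or leave them out, and each choice has different consequences.

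This matters more here than in a cohort where safety is secondary. The surgical sequence gives both drugs before surgery, craniotomy about two weeks later and radiotherapy three weeks after that; the main-cohort lead-in did not test it. Section 7.3.4 also counts only patients who received drug and underwent re-resection, whereas Sections 7.2.1 and 7.3.3 include everyone dosed. Under 7.3.4, a patient whose pre-operative toxicity prevents surgery would drop out of the surgical safety analysis.

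**Working it through.** **1. Reproduce the plan's own figures.** Inputs from Section 3.5.1: prior Beta(2,3) and x toxicities in n patients. The posterior is Beta(2 + x, 3 + n − x), and the quantity of interest is the probability that the rate exceeds a threshold.

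| x/n | Posterior | Printed | Rate > 40% | Rate > 30% |
|---|---|---|---|---|
| 2/3 | Beta(4,4) | 0.71 | 0.710 | 0.874 |
| 4/6 | Beta(6,5) | 0.83 | 0.834 | 0.953 |
| 5/9 | Beta(7,7) | 0.77 | 0.771 | 0.938 |
| 7/12 | Beta(9,8) | 0.86 | 0.858 | 0.974 |
| 8/15 | Beta(10,10) | 0.81 | 0.814 | 0.967 |
| 9/18 | Beta(11,12) | 0.77 | 0.772 | 0.961 |
| 11/21 | Beta(13,13) | 0.85 | 0.846 | 0.983 |
| 12/24 | Beta(14,15) | 0.81 | 0.813 | 0.979 |

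All eight printed values reproduce at 40% and none at 30%. The arithmetic of the rule is sound, but Section 3.5.1 names both thresholds.

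**2. Cohorts monitored separately.** With 16 surgical patients, the printed looks that can occur are 3, 6, 9, 12 and 15. Crossing probabilities come from an exact binomial recursion: add patients one at a time at true rate p, remove the paths that reach the boundary at each look, and sum what was removed. The first look contributes 3p²(1 − p) + p³; at p = 0.40 that is 0.288 + 0.064 = 0.352. The later looks at p = 0.40 add 0.028, 0.065, 0.009 and 0.027, giving 0.480 (from unrounded terms).

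| True rate | Surgical, looks 3 to 15 | Main cohort, looks 3 to 24 |
|---|---|---|
| 20% | 0.114 | 0.115 |
| 30% | 0.265 | 0.278 |
| 40% | 0.480 | 0.532 |
| 50% | 0.714 | 0.798 |
| 60% | 0.891 | 0.953 |

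No boundary is printed at 16. There, 8/16 gives 0.755 and 9/16 gives 0.872. A 9/16 boundary would add nothing, because 9 events in 16 require at least 8 in the first 15, which has already crossed.

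**3. Cohorts pooled.** Patients 25 to 40 have no boundary. Masking is also possible. Take a pooled look at 24 with 8/12 surgical and 3/12 main-cohort toxicities: the count is 11/24, posterior Beta(13,16), probability above 40% = 0.695, below the 12/24 boundary. The surgical cohort alone, at 8/12, has posterior Beta(10,7) and probability 0.94, past its 7/12 boundary.

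**4. Surgical patients not counted.** If Section 3.5.1 covers only the 24 main-cohort patients, no surgical count can cross a boundary in that section.

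**5. Reach of Section 3.5.2.** The surgical cohort opens after the 6-patient lead-in, so between 0 and 12 − 6 = 6 of the first 12 treated could be surgical. It is one look, for CNS toxicity only.

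**The case against.** A reader might infer that the surgical cohort has no stopping rule at all, or that the chance of a formal stop is zero. The documents do not support that. Section 3.1.2 refers to the whole of Section 3.5, and Section 3.5.2 is not limited to the main cohort; four surgical CNS events among the first 12 treated would by themselves halt the trial. Section 8.4 has the DSMC evaluate all SAEs, and Section 8.6.1 gives quarterly review with extra reviews possible. The zero applies only to Section 3.5.1 read literally.

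The sponsor can also say that Section 3.5.1 opens by speaking of the phase II portion, that Section 7.2.3 labels the surgical cohort a phase II trial, and that boundaries at 3 to 15 patients are already printed. On that reading the intended rule is the one proposed below. It is a reasonable reading, but nothing in the text selects it over pooling or exclusion.

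Three further points stand. A crossing only means that termination will be considered. At the 40% level that Section 3.5.1 calls unacceptable, separate monitoring flags with probability only 48%. And Section 8.4 defines study treatment as the two drugs and radiation, so a complication attributed to the craniotomy alone might not count as related.

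It is also tempting to conclude that the cohort needs its own lead-in. The documents do not establish that: it opens only after the same drugs, doses and radiotherapy have passed the main-cohort lead-in.

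**Conclusion.** The point holds as a gap in the overall-toxicity rule. Section 3.5.1 provides neither boundary nor counting rule for 16 patients for whom safety and tolerability are a primary objective, and what else may reach them is a single CNS look and DSMC review without a numeric criterion. The consequence depends on the reading: a flag probability of 48% to 89% at true rates of 40% to 60% if the cohort is monitored alone, no boundary after patient 24 and possible masking if pooled, and no Section 3.5.1 flag if excluded.

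The crossing probabilities assume independent patients with a constant toxicity rate and complete outcomes at each look. The true rates are illustrative; the documents give no expected rate for this cohort. The masking example concerns one pooled look with 12 patients from each cohort; whether an earlier pooled look would have crossed depends on the order of events.

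**What to change.** In Section 3.5.1, state that the same Beta(2,3) rule and the printed boundaries at 3, 6, 9, 12 and 15 patients are applied to the surgical cohort separately from the main cohort, with related toxicity counted from the first pre-operative dose whether or not re-resection follows. Keep the existing table for the 24 main-cohort patients. State how perioperative events are classified for this count. In Section 3.5.2, state whether surgical patients enter the group of 12. In the same edit, reconcile the 30% wording with the 40% level, noting that only 40% reproduces the printed posteriors.

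The cost is a few sentences, using boundaries already printed and data already collected. The downside is an 11% to 27% chance of a non-binding review flag if the true rate is 20% to 30%, close to the 12% to 28% the plan already accepts for the main cohort.

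### The eight toxicity boundaries in Section 3.5.1 match no single posterior cut-off: 2 of 3 (0.710) triggers consideration of stopping, while 6 of 12 (0.716) and 10 of 21 (0.732) do not

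*Combined protocol and SAP*

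**What the plan says.** Section 3.5.1 (Phase II Safety Analysis) describes a "Bayesian-based rule for the probability that the rate of unacceptable toxicity exceeds a maximal tolerated level of 40" per cent. It adopts a Beta(2,3) "prior, which is prior information equivalent to two unacceptable toxicities observed in 5 treated patients". Early termination is then to be considered "based on a posterior probability (in parentheses), that the unacceptable toxicity rate exceeds 30" per cent. The list opens with "Termination will be considered if unacceptable toxicity is observed in" and gives "2 of 3 patients (0.71), 4 of 6 patients (0.83), 5 of 9 patients (0.77), 7 of 12 patients (0.86", followed by "8 of 15 patients (0.81), 9 of 18 patients (0.77), 11 of 21 patients (0.85), or 12 of 24 patients (0.81". Section 3.1.2 sets the timing: a "Bayesian monitoring approach, assessing safety with the accrual of every three additional patients". The 24 patients include the 6 from the Safety Lead-In.

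No section states the posterior value at which a count becomes a boundary. Section 8.5 only refers back to Section 3.5. Section 6.1.1 has a separate lead-in rule: 2 or more DLTs in the first 3 subjects halts the study, and 2 or more in the first 6 leads to redesign or stopping.

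**The concern.** A rule said to rest on a posterior probability should react in the same way to the same strength of evidence. Here the first look flags a posterior of 0.710, while two later looks pass over higher ones. A committee that sees 6 of 12 or 10 of 21 would hold stronger evidence of excess toxicity than the plan acts on after 3 patients, with no prompt to consider stopping.

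The out-of-line entry is also where most of the triggering occurs when the true rate is acceptable. With no cut-off stated, nobody can tell whether 2 of 3 is a deliberate exception or a slip. Nor can a boundary be derived for a review that falls between multiples of three, which is possible because Section 8.6.1 also has the DSMC review quarterly.

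**Working it through.** **Inputs.** All are from Section 3.5.1 except the look schedule (every 3 patients up to 24, Section 3.1.2): Beta(2,3) prior; two named limits, 40% and 30%; eight boundaries with printed posteriors.

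**Formula.** After x unacceptable toxicities in n patients the posterior is Beta(2+x, 3+n−x), and P(rate > t) is its upper tail at t. With whole-number parameters, P(Beta(a,b) > t) = P(Bin(a+b−1, t) ≤ a−1).

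**Step 1: reproduce the printed figures.** For 2 of 3 the posterior is Beta(4,4). At t = 0.40 this needs P(Bin(7, 0.4) ≤ 3) = 0.0280 + 0.1306 + 0.2613 + 0.2903 = 0.7102, printed as 0.71. All eight printed values reproduce to two decimals at 40%. None does at 30%, where 2 of 3 gives 0.874.

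**Step 2: look one event below each boundary (t = 0.40).**

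| n | Boundary | Posterior at boundary | Posterior one event lower |
|---|---|---|---|
| 3 | 2 | 0.7102 | 0.4199 |
| 6 | 4 | 0.8338 | 0.6331 |
| 9 | 5 | 0.7712 | 0.5744 |
| 12 | 7 | 0.8577 | 0.7161 |
| 15 | 8 | 0.8139 | 0.6675 |
| 18 | 9 | 0.7720 | 0.6244 |
| 21 | 11 | 0.8462 | 0.7323 |
| 24 | 12 | 0.8132 | 0.6950 |

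**Step 3: is there a common cut-off?** It must be no higher than the smallest value in the third column (0.7102, at 2 of 3) and above the largest in the fourth (0.7323, at 10 of 21). No number does both. Without the first look, the third-column minimum is 0.7712, so any cut-off above 0.7323 and up to 0.7712 gives the other seven boundaries. Both 6 of 12 and 10 of 21 can be reached without crossing an earlier boundary.

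**Step 4: does the 30% wording rescue the list?** No. At t = 0.30, 2 of 3 (0.874) triggers, while 6/12 (0.926), 7/15 (0.916), 8/18 (0.908), 10/21 (0.956) and 11/24 (0.951) do not.

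**Step 5: boundaries from one cut-off (t = 0.40).**
- 0.71: 2/3, 4/6, 5/9, 6/12, 8/15, 9/18, 10/21, 12/24 (two entries change).
- 0.75: 3/3, 4/6, 5/9, 7/12, 8/15, 9/18, 11/21, 12/24 (one entry changes).

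**Step 6: chance that the list triggers at some look.** This is an exact binomial recursion over the eight looks, for the Bayesian list alone. The first-look share is 3p²(1−p) + p³; at p = 0.30 that is 0.189 + 0.027 = 0.216.

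| True rate | As printed | of which at 2 of 3 | Cut-off 0.71 | Cut-off 0.75 |
|---|---|---|---|---|
| 20% | 11.5% | 10.4 points | 11.9% | 3.4% |
| 30% | 27.8% | 21.6 points | 30.0% | 15.9% |
| 40% | 53.2% | 35.2 points | 57.1% | 42.8% |
| 50% | 79.8% | 50.0 points | 82.8% | 74.6% |
| 60% | 95.3% | 64.8 points | 96.3% | 94.0% |

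**The case against.** The strongest reply is that nothing stated is broken. The printed posteriors are right at 40%, no uniform cut-off is promised, and termination is only to be considered. That stands in part: this is an incoherent and undocumented set of thresholds, not a miscalculated one, and the probabilities above are chances of triggering a review, not of stopping the trial. It does not remove the conflict, because the section says the decision rests on the posterior.

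A reader might go further and infer that the DSMC cannot apply the rule consistently. The documents do not support that: the rule is one explicit whole-number count per look and needs no posterior to be computed.

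A second reply is that extra caution at the first look is intended, since Section 6.1.1 also acts on 2 of the first 3 subjects. The counts do coincide, but the endpoints differ (DLT there, unacceptable toxicity here), and Section 3.5.1 gives no such reason. The overlap does limit the figures. The lead-in rule acts on the same first six patients, so the trial's overall chance of a safety halt is not the one tabulated. If DLTs occurred in 30% of patients (an assumption), 2 or more of 6 would occur with probability 1 − 0.7⁶ − 6(0.3)(0.7⁵) = 0.58.

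A third reply is that the practical effect is modest. Moving to 0.71 adds only 2.2 points at a true 30%. At a true 40%, the printed list reaches exactly 6 of 12 in 5.4% of trials and exactly 10 of 21 in 2.9%. This is fair, and it argues against ranking the point as a must-fix.

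**Conclusion.** The concern holds as an incoherence in the boundary list. No posterior cut-off produces all eight boundaries at either limit the section names, and the list acts at 0.710 while passing over 0.716 and 0.732. Seven boundaries form a consistent set; 2 of 3 is the exception. For the list alone, that look supplies 10.4 of 11.5 points of triggering at a true 20%, and 21.6 of 27.8 at 30%.

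This rests on the Beta(2,3) prior, the 40% limit, looks exactly every three patients, independent outcomes with a constant rate, and leaving out the lead-in DLT rule. Severity: should-fix.

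**What to change.** 1. In Section 3.5.1, first correct the sentence that ties the parenthesised posteriors to 30%; they reproduce only at 40%. The order matters. If the 30% wording stood, a cut-off of 0.71 or 0.75 would give 2/3, 3/6, 4/9, 5/12, 6/15, 7/18, 8/21, 9/24, which triggers with probability 52.5% at a true 30%.
2. State one posterior cut-off and derive all eight boundaries from it. The choice is the sponsor's:
   - 0.71 keeps 2/3 and changes 7/12 to 6/12 and 11/21 to 10/21 (30.0% at a true 30%). It is safer to print than 0.70, because 11/24 is 0.695 and rounds to 0.70, which would leave the last boundary open to dispute.
   - 0.75 changes only the first entry, to 3/3 (15.9% at a true 30%). That count would then differ from the 2-of-3 DLT count in Section 6.1.1, so the two sections should be read together.
   - Alternatively, keep 2/3 as a declared exception to a 0.75 cut-off and give the reason, for example alignment with the DLT rule in Section 6.1.1. The list then stays as printed.
3. Print the cut-off and the trigger probabilities, and say whether they include the lead-in rule.

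The cost is a short amendment to one section: a corrected percentage, a stated cut-off, and at most two changed boundary counts. Sample size and endpoints are unaffected. With 0.71, triggering at a true 30% rises by 30.0 − 27.8 = 2.2 points. With 0.75 it falls by 27.8 − 15.9 = 11.9 points, while triggering at a true 60% falls from 95.3% to 94.0%.
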